**7.3.2. Summary Measure**

Hgb at each assessment visit

The values will be summarized using mean, standard deviation, 95% CI, minimum, P25, median, P75, and maximum at each assessment visit by treatment group. Graphical summaries will be provided using mean and 95% CI over time. This will also be summarized by prior ESA type, prior ESA dose, and ERI subgroup.

Change from baseline at each assessment visit

The values will be summarized using mean, standard deviation, 95% CI, minimum, P25, median, P75, and maximum at each assessment visit by treatment group. Graphical summaries will be provided using mean and 95% CI over time. This will also be summarized by prior ESA type, prior ESA dose, and ERI subgroup.

Number (%) of subjects by Hgb change from baseline category at Week 4 - daprodustat

The number and percentage of subjects within each category will be provided only for daprodustat group and the categories will be classified into 6 (i.e., ≤-2, >-2 to -1, >-1 to 0, >0 to 1, >1 to 2, >2 g/dL). In addition, ‘within ±1 g/dL (i.e., ≤-1 and ≥1)’ and ‘over ±2 g/dL (i.e., <-2 and >2)’ categories will be provided. This will also be summarized by prior ESA type, prior ESA dose, and ERI subgroup.

Number (%) of subjects with Hgb within the target range at each assessment visit

The number and percentage of subjects with Hgb within, above and below the target range will be summarized at each assessment visit by treatment group. Graphical summaries over time will also be produced.

Time (%) in the Hgb target range during the primary efficacy evaluation period

The time (weeks and percentage) within/above/below the target range will be summarized by treatment group using mean, standard deviation, minimum, P25, median, P75, and maximum. Treatment differences (daprodustat – darbepoetin alfa) and the associated 95% CIs for the time (weeks and percentage) within the target range will also be provided. See Section 15.6.3 for details.

Number (%) of subjects who have an Hgb level of less than 7.5 g/dL

The number and percentage of subjects who have an Hgb level of less than 7.5 g/dL during the treatment period will be summarized by treatment group. On-therapy Hgb values observed in both scheduled and unscheduled visits will be included in the summary.

Number (%) of subjects who have an Hgb increase of more than 2.0 g/dL over any 4 weeks

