#### 15.4.1.1. Study Phases for Hgb Data

Treatment State	Definition
Pre-therapy	Date ≤ Randomization Date
On-therapy	Randomization Date < Date ≤ Treatment Stop Date + 1 day
Post-therapy	Date > Treatment Stop Date + 1 day

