**Flowchart for Hgb Analyses**

- This flowchart will be applicable, unless otherwise specified
  - Basically, scheduled visits between Day 1 and Week 52 will be applicable to this flowchart, but analyses including by-visit summaries may include other scheduled visits (ie. screening and follow-up visit).
- [1] Regarding partially evaluated Hgb values, the following summaries of Hgb will include unscheduled visits:
- Summary of Time (weeks and %) within Hgb target range during the primary efficacy evaluation period
  - Summary of Number (%) of subjects who have an Hgb level of less than 7.5 g/dL
  - Summary of Number (%) of subjects who have an Hgb level of more than 13.0 g/dL and number of episodes

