
 
For this reporting purpose, on-therapy Hgb values of central laboratory during Week 40 to Week 52, including unscheduled visits, will be used. However, if a central laboratory Hgb value is missing, a corresponding non-missing HemoCue Hgb value, which is associated with the identical subject number and visit, will be used.
 
Number of days that a subject’s Hgb is within the analysis range of 10.0-12.0 g/dL inclusive between Week 40 and 52, including any on-therapy Hgb values that were taken during this time period. Linear interpolation is used to estimate Hgb between visits, if a subject has an intermittent missing value (Rosendaal, 1993).
 
 
Illustration of calculation
 
  
 Hgb (g/dL)	Lab Date	Visit	Ref Day	Hgb Shift	Total shift (%) within range	Time in range (weeks)	
   
 9.9	01AUG2017	Week 40	0	NC	NC	NC	
 
 10.8	01SEP2017	Week 44	31	0.9 (=10.8-9.9)	total shift: 0.8 0.8/0.9=88.89%	(31-0)*0.8889/7 =27.56/7 (weeks)	
 
 missing	01OCT2017	Week 48	61	NA	NA	NC	
  
	Hgb (g/dL)	Lab Date	Visit	Ref Day	Hgb Shift	Total shift (%) within range	Time in range (weeks)	9.9	01AUG2017	Week 40	0	NC	NC	NC	10.8	01SEP2017	Week 44	31	0.9 (=10.8-9.9)	total shift: 0.8 0.8/0.9=88.89%	(31-0)*0.8889/7 =27.56/7 (weeks)	missing	01OCT2017	Week 48	61	NA	NA	NC
Hgb (g/dL)	Lab Date	Visit	Ref Day	Hgb Shift	Total shift (%) within range	Time in range (weeks)																						
9.9	01AUG2017	Week 40	0	NC	NC	NC																						
10.8	01SEP2017	Week 44	31	0.9 (=10.8-9.9)	total shift: 0.8 0.8/0.9=88.89%	(31-0)*0.8889/7 =27.56/7 (weeks)																						
missing	01OCT2017	Week 48	61	NA	NA	NC																						

Time in Target Range						
12.4	01NOV2017	Week 52	92	1.6 (=12.4-10.8)	total shift: 1.2 1.2/1.6=75%	(92-31)*0.75/7 =45.75/7 (weeks)
Overall time in the target range = (27.56 + 45.75)/7 = 73.31/7 = 10.47 (weeks)						
Percent time in the target range = 10.47/(92/7) = 79.68%						
NC: Not calculated, NA: Not available						

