
 
Hgb laboratory assessment date will be used to calculate a duration (Ref Day) between assessments.                             
 
Duration between assessments = [Hgb lab date] – [Hgb lab date of the previous measurement]
 
 
 
 
If a subject was withdrawn from the treatment before Week 40 so that the duration between Week 40 to Week 52 cannot be calculated, the subject will not be included in a summary.
 
Basically, the duration should be [Week 52 lab date – Week 40 lab date] unless a subject was withdrawn before Week 52. In this case, treatment stop date will be used instead of Week 52.
 
 
As an above example, suppose a subject has Hgb reading 9.9 g/dL on August 1st (Week 40), then reading if 10.8 g/dL on September 1st. The assumption is made that the week, between these scheduled assessments the subjects Hgb increases from 9.9 to 10.8 g/dL in a linear manner. The following steps are taken to calculate the time (days) the subject's Hgb was within target range (10.0 to 12.0 g/dL).                             
 
Calculate amount of Hgb shift (9.9 to 10.8 = 0.9 shift) and Hgb shift within range (0.8 out of shift is within range of 10.0 – 12.0)
 
Calculate percent of total shift (%) within range (0.8/0.9 = 88.89%)
 
Estimate the number of weeks since last visit within range (88.89% x duration between assessments = 88.89% x 31/7 weeks = 3.94 weeks within range)
 
 
 
 
If a subject has an intermittent missing Hgb assessment (on-therapy), the linear interpolation will be done by ignoring missing Hgb data.
 
To calculate overall time (weeks) in Hgb target range, the total days in range for each time period are added together and divided by 7.
 
The % of time in range between Week 40 and Week 52 for a subject will be calculated by calculating overall time (weeks) within range and dividing by the total duration (weeks) between Week 40 to Week 52. Similarly, the % of time above Hgb target range and % of time above and below Hgb target range will be calculated,
						

Dose Adjustment
Dose Adjustment Algorithm

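### Time in Hgb target range: for subjects withdrawn between Weeks 40 and 52 the denominator runs to the treatment stop date, but time is credited only between on-therapy Hgb dates, so within, above and below need not total 100%

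*SAP*

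**What the plan says.** SAP 15.6.3, Time in Target Range, uses on-therapy central laboratory Hgb from Week 40 to Week 52, including unscheduled values. HemoCue stands in only where the central value at the same visit is missing.

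- **Numerator.** Time is built from the intervals between one Hgb laboratory date and the previous one: "Linear interpolation is used to estimate Hgb between visits, if a subject has an intermittent missing value".
- **Denominator.** The percentage is obtained by "dividing by the total duration (weeks) between Week 40 to Week 52". For a subject withdrawn before Week 52: "In this case, treatment stop date will be used instead of Week 52".
- **Exclusion.** Only one is stated: "If a subject was withdrawn from the treatment before Week 40 so that the duration between Week 40 to Week 52 cannot be calculated".
- **Reporting.** SAP 7.3.2: "The time (weeks and percentage) within/above/below the target range will be summarized by treatment group". A between-arm difference with 95% CI is given for time within range.
- **On-therapy Hgb.** SAP 15.4.1.1 defines the window as "Randomization Date < Date ≤ Treatment Stop Date + 1 day".
- **Stop date.** Under SAP 15.6.1 it is the latest recorded stop date on daprodustat. For withdrawn darbepoetin alfa subjects it is an assumed date, the last injection plus 6 days.

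**The concern.** For a completer, numerator and denominator share the same first and last dates. For a subject withdrawn between Weeks 40 and 52, the denominator ends at the stop date and the credited time ends at the last on-therapy Hgb. Days between the two sit in the denominator and in no category, so time in range is understated. If the last Hgb falls on the stop date plus one day, which still counts as on-therapy, the total slightly exceeds 100%.

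The stop-date rule differs by arm, so the size of the mismatch can differ by arm too. A subject with only the Week 40 Hgb has no interval at all, and the SAP does not say how that subject is handled. At stake are a reported table whose three categories may not add up and a small error in a secondary treatment difference.

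**Working it through.** **1. The SAP's worked example (a completer).** Hgb is 9.9 on day 0, 10.8 on day 31, missing at Week 48, and 12.4 on day 92.

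- Within: (0.8/0.9) × 31 + (1.2/1.6) × 61 = 27.56 + 45.75 = 73.31 days
- Above: (0.4/1.6) × 61 = 15.25 days
- Below: (0.1/0.9) × 31 = 3.44 days
- Sum: 92 days. Within = 73.31/92 = 79.68%, as the SAP states. Above is 16.58% and below 3.74%, total 100%.

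**2. The same subject, withdrawn after the day-31 Hgb.** Credited time is 27.56 days within and 3.44 below. The stop days are assumptions.

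| Stop day | Within | Below | Total |
|---|---|---|---|
| 30 (Hgb on stop date + 1) | 91.9% | 11.5% | 31/30 = 103.3% |
| 37 | 74.5% | 9.3% | 31/37 = 83.8% |
| 45 | 61.2% | 7.7% | 31/45 = 68.9% |
| 58 | 47.5% | 5.9% | 31/58 = 53.4% |

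With the denominator ended at day 31, within is 88.9% and below 11.1%, total 100%, whatever the stop day.

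**3. The arm-specific stop date.** Take an always-in-range subject with Hgb on days 0 and 28 and both products last given on day 35. The result is 28/35 = 80% on daprodustat and 28/41 = 68% on darbepoetin alfa. Equal last-dose days give the widest contrast. Tablets are daily and injections weekly, so the last injection will often be some days earlier than the last tablet.

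**4. Size per arm (illustration).** From the protocol: 135 randomized per arm and 25% dropout. Assumed: dropout spread evenly over 52 weeks, 70% true time in range, Hgb on days 0, 28 and 56 only, no withdrawal-visit or unscheduled Hgb counted, one-Hgb subjects not calculated.

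- Withdrawn: 0.25 × 135 = 33.75. In Weeks 40–52: 33.75 × 12/52 = 7.79, of whom 2.60 before Week 44 (one Hgb) and 5.19 later.
- Included: 101.25 + 5.19 = 106.4. Affected: 5.19/106.4 = 4.88%.
- Mean credited share, daprodustat: (ln 2 + 2 ln 1.5)/2 = 0.752. Loss: 0.70 × 0.248 × 4.88 = 0.85 points.
- Darbepoetin alfa, stop date always 6 days later: (ln(62/34) + 2 ln(90/62))/2 = 0.673. Loss: 0.70 × 0.327 × 4.88 = 1.12 points; arm gap 0.27.
- Darbepoetin alfa, last injection 0–6 days before withdrawal (uniform, so the stop date is 0–6 days later): mean share 0.711. Loss: 0.70 × 0.289 × 4.88 = 0.99 points; arm gap 0.14.

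**5. Alternative: an Hgb on the last-dose or withdrawal day in both arms.** All 7.79 subjects are then included, 7.79/109.0 = 7.14%. The daprodustat loss is 0. On darbepoetin alfa with the full 6-day offset, the share is 1 − (6/84) ln 15 = 0.807 and the loss about 0.97 points. Averaged over offsets of 0–6 days, the share is 0.886 and the loss about 0.57.

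**6. Scale.** With an assumed SD of 25–35 points, the 95% CI half-width for the arm difference is 1.96 × SD × √(2/106.4) = 6.7–9.4 points. A gap of 0.14–0.27 is about 1–4% of that (0.14/9.4 to 0.27/6.7). A gap of 0.57–0.97 is about 6–14%.

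**The case against.** **The tail may be covered elsewhere.** The SAP never says in words that the numerator ends at the last Hgb. The flowchart for Hgb analyses is not reproduced in the available text, and the mock shells are separate documents. This limits the claim to the visible text. There, though, time is defined only between two Hgb dates and no carry-forward is given, so following the stated rules produces the mismatch.

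**A withdrawal-visit Hgb may close the gap.** Hematology is scheduled at early withdrawal, and the flowchart notes list the "Summary of Time (weeks and %) within Hgb target range during the primary efficacy evaluation period" among those that admit unscheduled values. For withdrawn darbepoetin alfa subjects the on-therapy window reaches 7 days after the last injection, so many such values would count and less would be lost. It is not a reliable cure. Protocol 5.4 places the visit after treatment is discontinued, the schedule gives it no day window, and only an Hgb on the stop date itself gives exactly 100%. The HemoCue-only visits (Weeks 42, 46, 50) are excluded by default in SAP Appendix 3.

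**One-Hgb subjects.** A reader might infer that they score 0%, which on the assumptions above would make arm means 2.5 points low (0.70 × 0.499 × 7.14) and 2.8 low (0.70 × 0.551 × 7.14). That reading is possible but less likely. The example marks its first row NC, with the legend "NC: Not calculated, NA: Not available", and SAP 7.3.4 bases secondary summaries on available, observed data. Neither settles the case, because NC there labels a row of a subject who still receives 79.68%.

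**Arm bias.** A reader might also infer a bias against one arm. The documents do not support a direction. The illustrated gap depends on last-dose timing and on which withdrawal-visit values count. Nor does any text require the three summaries to total 100%.

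**Conclusion.** The rule as written gives a wrong percentage for subjects withdrawn between Weeks 40 and 52; this is more than a missing detail. Time in range is usually understated and can be slightly overstated. The handling of one-Hgb subjects is, by itself, only unspecified.

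The effect is minor. Under the assumptions in step 4 of the working, about 5 of 106 subjects per arm are affected. Arm means are about 0.85 points low on daprodustat and 1.0–1.1 on darbepoetin alfa, a gap of about 0.1–0.3 points with no certain direction. With a stop-day Hgb in both arms the losses are 0 and about 0.6–1.0 points. Confidence is high that the two end dates can differ and low on the size, because the number of subjects affected cannot be known from the documents.

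Protocol 9.3.3 treats other secondary endpoints as complementary or exploratory, without multiplicity adjustment. Nothing here reaches the primary or principal secondary analysis, neither of which uses this derivation.

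**What to change.** In SAP 15.6.3, for both arms, end the time-in-range denominator at the date of the last on-therapy Hgb used in the interpolation, so that the three categories total 100%. As an accompanying clarification, state that a subject with only one such Hgb is not evaluable, and report that number by arm. The stop-date rules in SAP 15.6.1 can stay as they are for exposure and compliance.

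The cost is two sentences and one derived date, with no new data. There are two downsides. A few one-Hgb subjects leave the summary (about 2.6 per arm in the illustration, fewer where a withdrawal-visit Hgb counts). Withdrawn subjects are also summarised over a shorter period than completers, yet weigh the same. Carrying the last Hgb forward to the stop date would also total 100%, but it credits time with no measurement behind it: within range would be 90.7% at stop day 37 and 94.1% at day 58 in the example, against 88.9% observed.

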**Dose Adjustment**

Illustration of dose adjustment algorithm (24-week case)

Visit (Example)	Treatment Start date/ Stop date	Duration	HemoCue Hgb (g/dL)	Dose (mg)	(FL_A)	(FL_B)	(FL_C)
					Adjustment	Over 13 g/dL	Inter-ruption
Day 1	01FEB2017/ 01MAR2017	29	11.1	4	N	N	N
Week 4	02MAR2017/ 15MAR2017	14	11.4	4	N	N	N
Week 8	02APR2017/ 01MAY2017	30	11.8	2	Y	N	N
Week 12	02MAY2017/ 01JUN2017	31	13.4	0	Y	Y	Y
Week 16	02JUN2017/ 01JUL2017	30	12.6	0	N	N	Y
Week 20	02JUL2017/ 01AUG2017	31	11.7	1	Y	N	N
Week 24	-	-	12.3	-	-	N	-

For programmers, note that the flags are for the purposed of illustration, and are not intended to imply any type of requirement.

For summary tables, further details are described within the next items;

- 'Duration (days) of treatment interruption due to Hgb >13.0 g/dL'
- 'Dose adjustment'

**Duration (days) of Treatment Interruption due to Hgb >13.0 g/dL**

Calculation of duration of treatment interruption due to Hgb >13.0 g/dL will be based on the dose adjustment algorithm defined in the protocol.

- Duration (days) = Sum of [Duration]n  
 where  
 [Duration]n represents exposure duration at visit n to meet the following.
  - Treatment interruption is made due to HemoCue Hgb over 13.0 g/dL and consecutive until treatment is resumed.

In the above illustration, duration = 61 (days), from Week 12 and 16 visit records.

**Dose Adjustment**

Calculation of frequency of dose adjustment will be based on the above algorithm.

- Number of dose adjustment will be counted for each subject as follows:
  - Counts of adjustment flag = 'Y'

**15.6.4. Safety**

Adverse Events
AE up to Week 4
Cut-off date of Week 4 for individuals will be based on Week 4 visit date which is associated with the earliest date throughout Week 4 records (i.e., SDTM.SV.STDTC).
AEs of Special Interest (AESIs)

AESIs are manually-selected at patient-level (i.e. following case-by-case review by members of the SRT including representatives from the local Japan team) and not at preferred term level.
 
AESI categories are classified as follows:
 
 
• Thrombosis and/or tissue ischemia secondary to excessive erythropoiesis
 
• Death, myocardial infarction, stroke, heart failure, thromboembolic events, thrombosis of vascular access
 
• Cardiomyopathy
 
• Pulmonary artery hypertension
 
• Cancer-related mortality and tumor progression and recurrence
 
• Esophageal and gastric erosions
 
• Proliferative retinopathy, macular edema, choroidal neovascularization
 
• Exacerbation of rheumatoid arthritis
 
 
Thrombosis and tissue ischemia events will be considered to be secondary to excessive erythropoiesis if during the window of [AE start date – 30 days, AE start date +15 days] any one of the following 3 events occurs:
 
 
• Any Hgb value > 13 g/dL
 
• Hgb increase > 2 g/dL over 2 weeks
 
• Hgb increase > 4 g/dL over 4 weeks
 
 
Note: Thrombosis and tissue ischemia events that need to be considered against the above 3 Hgb events will be identified by the case-by-case review.
 
Note: HemoCue and central laboratory values will be considered separately. Unscheduled Hgb values will also be used in the assessment of secondary to excessive erythropoiesis if available.
 
Note: For the second two bullets, all Hgb values that have an assessment date within the window of [AE start date – 58 days, AE start date + 15 days] will be considered.

Laboratory Parameters
Imputation

 
• If a laboratory value which is expected to have a numeric value for summary purposes, has a non-detectable level reported in the database, where the numeric value is missing, but typically a character value starting with '<x' or '>x' (or indicated as less than x or greater than x in the comment field) is present, the number of significant digits in the observed values will be used to determine how much to add or subtract in order to impute the corresponding numeric value.             
 
○ Example 1: 2 Significant Digits = '< x' becomes x – 0.01
 
○ Example 2: 1 Significant Digit = '> x' becomes x + 0.1
 
○ Example 3: 0 Significant Digits = '< x' becomes x – 1
 
 
 
• The following laboratory values will not be applicable for this imputation:             
 
○ Hgb, serum iron, serum ferritin, serum transferrin, TIBC, UIBC, TSAT, and Hcpidin
 
 
 

Laboratory Parameters

 
The default convention for reporting of clinical laboratory units will be the international system of units (SI units).
 

Lipid Parameters

 
LDL/HDL cholesterol ratio will be derived from the following equation. 
 
LDL/HDL cholesterol ratio = LDL cholesterol (mmol/L) / HDL cholesterol (mmol/L)
 
 
 

Log-Transformation

 
Lipid parameters will be log-transformed and the percent change from baseline will be reported. Based on literature review the distributions of hepcidin and TSAT are skewed and require a log-transformation. Other endpoints may also be log-transformed if deemed appropriate (See Section 5.2).
 

Others

 
For summaries of the absolute neutrophils and lymphocytes count, PCI cutoffs will be calculated by multiplying the percentages given for each subject by the absolute white blood count.
 

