2.2. Background

Renal anemia is diagnosed in many patients with CKD, and the prevalence of renal anemia increases with progression of CKD [Akizawa, 2011]. Causes of anemia in CKD patients include absolute or relative deficiency of erythropoietin (EPO), shortened erythrocyte survival, and reduced iron availability. Anemia is further exacerbated by chronic blood loss associated with hemodialysis procedure, infection, and functional hemolysis [Japanese Society for Dialysis Therapy, 2016].

Daprodustat is a hypoxia-inducible factor-prolyl hydroxylase inhibitor that is currently being developed as a treatment for renal anemia. Data in Japanese patients have been collected from a Japanese Phase II 4-week treatment study in Japanese hemodialysis (HD) subjects (PHI116099: 97 Japanese subjects), an international multi-center Late Phase II 24-week treatment study in HD subjects (PHI113633: including 24 Japanese subjects), and an international multi-center Late Phase II 24-week treatment study in Non-dialysis subjects (PHI113747: including 42 Japanese subjects). In these clinical studies, daprodustat increased endogenous EPO, reduced hepcidin, and increased Hgb in HD and ND subjects including Japanese subjects. In addition, daprodustat increased Hgb at lower blood EPO concentrations than existing ESAs.

Summaries of findings from both clinical and non-clinical studies conducted with daprodustat can be found in the daprodustat Investigator's Brochure (IB) and IB supplement(s) (if applicable). A benefit: risk assessment, including risk mitigation strategies, is outlined in Section 4.6.

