**7.4.3. Population of Interest**

The exploratory efficacy analyses will be based on the ITT population, unless otherwise specified.

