**7.4.4. Strategy for Intercurrent (Post-Randomization) Events**

Any intercurrent events are taken to be irrelevant for exploratory endpoints and the exploratory endpoints will be summarized based on available and observed data.

Analysis of change from baseline in the respective iron parameter at each assessment visit will follow the strategy below.

Intercurrent events	Strategy
Study withdrawal / Intermittent missing	The following hypothetical scenario is considered to assess what would have happened if the event did not occur. Analysis using MMRM assume missing at random mechanism, that is the observations of missing depend on just observed values, not on unobserved values.

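### The SAP leaves hepcidin results beyond an assay limit without a numeric value; if such results occur, the exploratory hepcidin ratio is pulled towards 1

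*SAP*

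**What the plan says.** SAP 15.6.4 (Laboratory Parameters, Imputation) deals with results that should be numeric but are non-detectable, "where the numeric value is missing, but typically a character value starting with" a less-than or greater-than sign. For these, "the number of significant digits in the observed values will be used to determine how much to add or subtract". The worked examples subtract 0.01 or 1 from a less-than limit and add 0.1 to a greater-than limit, depending on the reported precision.

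The section then states "The following laboratory values will not be applicable for this imputation" and names "Hgb, serum iron, serum ferritin, serum transferrin, TIBC, UIBC, TSAT, and Hcpidin" (the last is hepcidin, misspelled). It gives neither a reason for the exceptions nor a substitute rule. By contrast, SAP 15.6.5 does set a rule for non-quantifiable drug concentrations: they become zero.

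Hepcidin change from baseline is an exploratory endpoint (Protocol 3, SAP 2.2). It is summarised on observed data and analysed on the log scale by a mixed model for repeated measures (MMRM; SAP 7.4.2, 7.4.5.1), giving an adjusted ratio with a 95% CI. SAP 7.4.4 states "Analysis using MMRM assume missing at random mechanism", and SAP 7.4.3 states "The exploratory efficacy analyses will be based on the ITT population, unless otherwise specified". Protocol 2.2 reports that in earlier studies "daprodustat increased endogenous EPO, reduced hepcidin, and increased Hgb in HD and ND subjects including Japanese subjects".

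**The concern.** A hepcidin result reported as `<x` is absent from the analysis because it is low. Its absence depends on the value that was not observed, which is what SAP 7.4.4 assumes away when it defines missing at random. If the drug lowers hepcidin, such results fall more often in the daprodustat arm. Removing them raises the daprodustat geometric mean more than the darbepoetin alfa one, and the reduction is understated.

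The exception also covers `>x`. Losing high hepcidin values, which would come mainly from the control arm, would pull the ratio in the same direction.

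Baseline is affected separately. Under the Time and Events Table, hepcidin is first sampled on Day 1 and not at screening, so the fallback in SAP 5.2 to an earlier pre-dose value normally has nothing to use. A below-limit Day 1 value leaves the baseline missing, and the subject leaves the change analysis.

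What is at stake is the estimate for a named mechanistic biomarker, which could be read as a weaker drug effect than the true one.

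**Working it through.** The plan states no figure for censored biomarker results, so there is nothing of its own to reproduce. The documents also give no assay limit, hepcidin SD, within-subject correlation, effect size or expected share of `<x` results. All of these are assumed below and varied.

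**Inputs.** From the documents: log-scale analysis, MMRM with baseline and baseline-by-visit terms, unstructured covariance, five post-baseline visits (Weeks 4, 16, 28, 40, 52), and direction of effect ("daprodustat increased endogenous EPO, reduced hepcidin, and increased Hgb in HD and ND subjects"). Assumed: log-SD s = 0.6 or 1.0; correlation between visits 0.4 or 0.7; true geometric mean ratio 1.0, 0.70 or 0.50; 1%, 5%, 10% or 20% of daprodustat values below the limit.

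**Step 1: one visit, censored values dropped.** If a fraction p of a normal distribution on the log scale is cut from below at z = Φ⁻¹(p), the mean of the rest rises by s·φ(z)/(1 − p). The control arm has the same limit, so its cut-off is z + ln(ratio)/s.

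Example with s = 1.0, ratio 0.50, p = 10%:
- Daprodustat: z = −1.2816, φ(z) = 0.1755, shift 0.1755/0.90 = 0.1950.
- Control: z = −1.2816 − 0.6931 = −1.9747, fraction below limit 2.4%, φ = 0.0568, shift 0.0568/0.9758 = 0.0582.
- Apparent ratio: 0.50 × exp(0.1950 − 0.0582) = 0.573.

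At 5%, 10% and 20% with s = 1.0 the apparent ratios are 0.543, 0.573 and 0.622. With s = 0.6 they are 0.531, 0.555 and 0.597.

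**Step 2: the planned type of model.** The single-visit figures overstate the effect on the MMRM, which uses baseline and correlated visits. The model was fitted by maximum likelihood to 60,000 simulated subjects per scenario. Values below the limit were set to missing, and subjects with a censored baseline were dropped. Week 52 ratios, with ranges over both SDs and both correlations:

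| Daprodustat values below limit | True 0.50 | True 0.70 |
|---|---|---|
| 1% | 0.50-0.51 | 0.70-0.71 |
| 5% | 0.51-0.54 | 0.71-0.72 |
| 10% | 0.53-0.56 | 0.73-0.75 |
| 20% | 0.55-0.60 | 0.75-0.78 |

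With a true ratio of 1.0 the estimates stay at 0.99-1.01. The loss differs between arms once there is an effect: at true ratio 0.70, 10% below the limit on daprodustat goes with 3-5% on control.

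**Step 3: substitution instead of dropping (single visit, 5% / 10% / 20%, true ratio 0.50).**

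| Value given to `<x` | s = 0.6 | s = 1.0 |
|---|---|---|
| The limit x | 0.506 / 0.514 / 0.532 | 0.509 / 0.520 / 0.544 |
| x/2 | 0.490 / 0.482 / 0.470 | 0.495 / 0.493 / 0.495 |

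Both are closer to 0.50 than dropping is. The limit errs towards no effect; x/2 errs the other way, more so at the smaller SD.

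**The case against.** The strongest reply is that this is a documentation gap with a conditional consequence. SAP 15.6.4 says only that its imputation does not apply to these analytes. It never says the results are discarded, and it is not known that any will occur. That stands, and the point is worded conditionally for that reason. It does not remove the need for a rule: the SAP itself describes the numeric field as missing, so followed as written the result drops out, and any other handling would be an unwritten choice affecting a treatment comparison.

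It is also fair that the error is conservative (none arises without a true effect), that the MMRM recovers part of the loss, and that the endpoint enters no confirmatory test.

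Three stronger readings are tempting, and the documents do not support them:
- **Ferritin is biased too.** Ferritin also lacks a rule, but neither document says daprodustat lowers it, and it is analysed untransformed, so the ratios above do not apply. Entry requires ferritin above 100 ng/mL or TSAT above 20% (Protocol 5.1), which makes undetectable ferritin look unlikely, although the 'or' does not exclude low values.
- **The baseline loss favours one arm.** Day 1 samples precede treatment, so below-limit baselines are expected equally in both arms. The cost is subjects, not a difference between arms.
- **The primary analysis is exposed because Hgb is on the list.** With entry at 9.5-12.5 g/dL and discontinuation below 7.5 g/dL, Hgb beyond an assay limit is implausible.

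**Conclusion.** The point holds for hepcidin, conditionally. The SAP exempts it from the only rule that gives `<x` and `>x` results a number and puts nothing in its place. If below-limit results occur and daprodustat lowers hepcidin as the protocol says, the ratio moves towards 1. For a true ratio of 0.50, the planned type of model would move by about 0.01-0.04, 0.03-0.06 and 0.05-0.10 at 5%, 10% and 20% censoring on daprodustat. It would move by about 0.01 or less at 1%, and not at all with no censoring. These sizes rest entirely on the assumed SD, correlation, effect and rate; only the direction comes from the documents. A reader might infer that the hepcidin result is certain to be biased; without an assay limit or a rate, that cannot be said. The primary and principal secondary conclusions are unaffected. Severity is minor.

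**What to change.** Before unblinding, amend SAP 15.6.4 as follows:
- Take hepcidin off the exception list.
- Set `<x` to a stated positive value (x/2, or x itself) and `>x` to x, at baseline and post-baseline. Do not rely on the variant that subtracts 1: it turns `<1` into 0, which cannot be log-transformed.
- State the hepcidin assay limits and report the number of `<x` and `>x` results by arm and visit.
- If censoring is material, add a censored-likelihood (Tobit) analysis as a check. Fix the trigger in advance; about 10% of an arm at a visit is one possible choice.

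The cost is a few SAP sentences, a small derivation and one count table. The downside is that single-value substitution understates variance and can bias the ratio slightly in either direction: for a true 0.50 at log-SD 0.6, x/2 gives 0.47-0.49 and the limit gives 0.51-0.53. That is why the censored-likelihood check is needed when many values are affected.
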